9.2.2 Contraception Requirements

Contraception requirements must be assessed by the investigator on a case by case basis. Where applicable, the patient or their partner must use highly effective contraception for the duration of the study and for three months thereafter.

To be eligible for the trial, male participants who are fertile (i.e., after puberty unless permanently sterile by bilateral orchidectomy) must agree that they are willing to use male contraception (e.g., condom) or remain sexually abstinent during the trial and for 3 months after the last dose.

Where applicable, females of childbearing potential (i.e., fertile, following menarche and until becoming postmenopausal for ≥ 12 consecutive months, unless permanently sterile by hysterectomy, bilateral salpingectomy, or bilateral oophorectomy per the definition of woman of childbearing potential) must use highly effective birth control method for the duration of the trial and for 3 months thereafter. Highly effective methods of birth control are defined as those, alone or in combination, that result in a low failure rate

Study Code: GWND19002
EudraCT Number: 2019-001605-24
Clinical Protocol V2 18Dec19

(i.e., less than 1% per year) when used consistently and correctly.⁶⁶ Such methods include:

- Combined (estrogen and progestogen containing) hormonal contraception associated with the inhibition of ovulation^a:
 - Oral.
 - Intravaginal.
 - Transdermal.
- Progestogen-only hormonal contraception associated with inhibition of ovulation^a:
 - Oral.
 - Injectable.
 - Implantable^b.
- Intrauterine devices^b
- Intrauterine hormone-releasing systems^b.
- Bilateral tubal occlusion^b.
- Vasectomized partner^{bb}, provided that partner is the sole sexual partner of the patient of childbearing potential and that the vasectomized partner has received medical assessment of the surgical success.
- Abstinence, as referenced above, is only acceptable as true abstinence, i.e., when this is in line with the preferred and usual lifestyle of the patient; periodic abstinence (e.g., calendar, ovulation, symptothermal, and postovulation methods) and withdrawal (coitus interruptus), spermicides only, and lactational amenorrhea method are not acceptable methods of contraception.⁶⁷

Serum pregnancy tests will be performed for any patients of childbearing potential at RCT Visit 9 and OLE Visit 8; patients must test negative for pregnancy to be eligible for the trial. Additional pregnancy tests must be performed during the treatment period if considered clinically indicated by the investigator.

^a The effect of GWP42003-P on oral contraceptives has not been investigated. GWP42003-P is not an inducer of CYP3A4 and therefore is not expected to alter the PK of hormonal contraceptives.

^b Contraception methods that are considered to have low user dependency

^{bb} Provided that partner is the sole sexual partner of the trial patient of childbearing potential and that the vasectomized partner has received medical assessment of the surgical success.

Study Code: GWND19002
EudraCT Number: 2019-001605-24
Clinical Protocol V2 18Dec19

9.2.3 Concomitant Medication

Details of all current medications will be recorded during the RCT. Any changes in concomitant medication during the trial must be recorded on the eCRF at trial visits. Changes in concomitant medications are allowed, but increases in the dose of medications that affect liver function should be discussed with the medical monitor. Introduction of new medications is allowed, but introduction of new psychotropic and/or central acting agents intended as long-term treatment requires prior discussion with the medical monitor.

9.2.4 New Medical History

Any changes to medical history since the RCT will be recorded.

9.2.5 Menstruation

Any changes in menstrual cycles since the RCT will be captured at the end-of-treatment visit.

9.2.6 Physical Examination

Physical examinations will include body weight measurements. At Visits 8, 10, 12 and 14 height will be collected. If an accurate measurement of height is not possible, an estimate should be provided.

9.2.7 12-Lead Electrocardiogram

Triplicate ECGs will be performed after 5 minutes of rest. Triplicate ECGs should be taken as close together as possible. An ECG machine will be provided to all centers, and all ECGs will be reviewed by a central reader. The central reader will provide a report within 24 hours of collection of the ECG. Additional alerts will be sent to the center in the case of clinically relevant abnormalities. The central reader will provide measurements and an overall assessment to support the investigator in his/her final assessment. If needed, the investigator may update clinical relevance based on patient files, medical history, and any clinical symptoms. The central reader can be supportive for any discussions on patient outcomes. Any abnormal findings considered to indicate significant medical history or AEs must be recorded appropriately on the eCRF. In addition to the scheduled assessments, additional ECG measurements can be taken at any time during the trial, if clinically indicated.

Study Code: GWND19002
EudraCT Number: 2019-001605-24
Clinical Protocol V2 18Dec19

9.2.8 Vital Signs

Vital sign measurements (blood pressure and pulse rate) will be taken in a sitting position at rest for 5 minutes. Blood pressure should be recorded using the same arm throughout the trial, where possible.

9.2.9 Clinical Laboratory Sampling

The investigator should use his/her judgment and knowledge of the patient to determine when to best collect the blood and urine samples in order to mitigate the risk that invasive procedures may cause the patient to become stressed, thereby affecting the results of other patient assessments.

Routine laboratory tests will include hematology, biochemistry, and urinalysis (provided urine can be obtained), IGF-1 levels, and a serum pregnancy test (if appropriate). Analysis of all clinical blood samples and pregnancy tests will be conducted at a central clinical laboratory.

Urine samples for biochemistry will be analyzed at the trial center by use of a dipstick, with any relevant findings being sent for further urinalysis at the central laboratory (urinalysis, microscopy, culture, and sensitivity, as applicable). In cases where urine samples cannot be analyzed at the center due to local regulations, a full set of urine samples should be sent to the central laboratory for analysis. Urine sample volume requirements and processing procedures will be detailed in a separate laboratory manual.

The investigator and trial monitor will be provided with a list of the normal ranges used by the testing laboratory for all variables assayed during the trial and a statement of accreditation (or similar) for the laboratory.

The investigator should be aware of blood sampling volume restrictions, particularly for patients with low weight, and if additional monitoring is required (maximum total daily volume of 0.85mL/kg of body weight^{68,69} maximum 4-week period volume of 2.55 mL/kg of body weight, and maximum 8-week period volume of 50 mL).

Clinical laboratory sample parameters are detailed in [Table 9.2.9-1](#).

Study Code: GWND19002
 EudraCT Number: 2019-001605-24
 Clinical Protocol V2 18Dec19

Table 9.2.9-1 Biochemistry, Hematology, and Urinalysis			
Biochemistry (Serum)¹	Hematology (Whole Blood)¹	Urinalysis (Urine)²	Pregnancy Test (Serum)¹
Alanine aminotransferase ³	Hematocrit	Blood	Serum
Albumin ³	Hemoglobin	Glucose	
Alkaline phosphatase ³	Mean cell volume	Nitrites	
Aspartate aminotransferase ³	Mean corpuscular hemoglobin	pH	
Calcium	Platelets	Protein	
Creatine kinase	Red blood cell count	White blood cells	
Creatinine	White blood cell count with automated differential	Bilirubin	
Creatinine clearance	Prothrombin time and INR (plasma) ⁵	Ketones	
Gamma-glutamyl transferase ³		Specific gravity	
Glucose		Urobilinogen	
Human chorionic gonadotropin			
HDL-cholesterol			
IGF-1 ⁴			
Potassium			
Prolactin			
Sodium			
Total bilirubin ³			
Total protein ³			
Triglycerides			
Urea (blood urea nitrogen)			

HDL = high-density lipoprotein; INR = international normalized ratio.

¹ Analyzed at a central laboratory.

² Analyzed at the trial center by use of a dipstick (if allowed per local regulations).

³ Hepatic function monitoring panel.

⁴ Visits 1, 8, 10 and 14 only; IGF-1 laboratory results to remain blinded throughout the trial.

⁵ To be requested if ALT or AST > 3 × ULN after Visit 1 (to evaluate IMP discontinuation criteria)

Investigators at trial centers will be notified of laboratory test results. All laboratory results will be reviewed, and the reports will be signed and dated by the investigator. Any results considered to be of clinical significance must be addressed and followed up, as clinically appropriate. Per protocol requirements, in addition to the pre-scheduled biochemistry, further hepatic function monitoring may be needed. In cases where after Visit 1, ALT or AST are > 3 × ULN, international normalized ratio (INR) testing must be requested. If only the hepatic function monitoring panel was requested and ALT or AST > 3 × ULN, both INR and hematology panel (eosinophils) must be requested. All

Study Code: GWND19002
EudraCT Number: 2019-001605-24
Clinical Protocol V2 18Dec19

laboratory results considered to represent an AE must be documented on the eCRF. For reporting and follow-up of potential cases of drug-induced liver injury, see [Section 12.8](#).

Repeat samples will be taken, if required, for clinical follow-up or if the sample is lost or damaged. Any abnormal end-of-treatment clinical laboratory result of clinical significance must be repeated at regular intervals until it returns to normal or until the investigator is satisfied that the abnormality is not related to GWP42003-P and needs no further investigation.

Additional samples may be collected, as needed, e.g., for monitoring of hepatic function (hepatic function monitoring panel) (see [Section 8.1.2](#) and [Table 9.2.9-1](#)).

Blood sample volume requirements and processing procedures will be detailed in a separate laboratory manual; the maximum cumulative amount of blood taken in any 4-week period will be 2.55 mL/kg of body weight and will not exceed a total of 50 mL within any 8 week period^{68,69} taking into account possible repeat tests. The patient/caregiver must be advised that it may not be safe for the patient to undertake further blood tests within 1 month of any trial-related blood draws and to inform the investigator if the patient suffered any blood loss during the 1-month period leading up to a planned blood draw.

9.2.10 Randomization and Trial Supply Management System

The RTSM system will be used to manage the IMP supply. The RTSM system information can be accessed via the eCRF.

A member of the trial team must register in the eCRF each clinic visit in order to:

- Obtain dispensing information (Visits 1, and 4 through 14 [end of treatment/withdrawal visit]).
- Provide completion/taper/early termination information (Visit 14/the end of treatment/withdrawal visit, or Visit 15 [end of taper], as applicable).

Training will be given to all centers prior to the start of the trial.

9.2.11 Dosing Schedule/Compliance Review

Caregivers will be provided with a dosing schedule. Caregivers will be asked to confirm dosing in the dosing schedule daily from Visit 1 through Visit 15 (end of taper). Dosing compliance will be reviewed at each clinic visit. Any discrepancies will be discussed with the caregiver and documented accordingly within the patient's source documents.

Study Code: GWND19002
EudraCT Number: 2019-001605-24
Clinical Protocol V2 18Dec19

As part of the compliance review, caregivers will be asked at the visits about the time of GWP42003-P administration in relation to meals.

9.2.12 Questionnaires and Assessments Completed at Scheduled Visits

Caregiver questionnaires should be completed by the identified caregiver, nominated at Visit 1 of the RCT. The same person should answer/complete the questionnaires/assessments in order to maintain consistency. Questionnaires should be completed during the scheduled visits. The nominated caregiver must have given consent to complete the QoL questionnaires prior to the completion of the questionnaires.

To ensure consistency, investigator-completed questionnaires should be completed for each patient by the same investigator throughout the trial. Investigators must have completed the sponsor-specified training for each questionnaire before any questionnaires are completed.

9.2.12.1 Rett Syndrome Behaviour Questionnaire

The RSBQ is a caregiver-completed questionnaire that measures the frequency of current disease characteristics (45 items) that may or may not apply to the patient. Each item is rated on a 3-point numerical scale; 0 indicates an item that is ‘not true as far as you know,’ 1 indicates an item is ‘somewhat or sometimes true,’ and 2 indicates an item that is ‘very true or often true.’ The total maximum score is 90, and higher total scores represent greater severity. It encompasses 8 subscales: general mood, breathing problems, hand behaviors, face movements, body rocking/expressionless face, night-time behaviors, anxiety/fear, and walking/standing.⁵⁵

9.2.12.2 Children’s Sleep Habit Questionnaire

This is a caregiver-completed sleep screening instrument designed for school-aged children.⁷⁰ CSHQ includes 33 items within 8 subscales reflecting the following sleep domains: 1) Bedtime Resistance; 2) Sleep Onset Delay; 3) Sleep Duration; 4) Sleep Anxiety; 5) Night Wakings; 6) Parasomnias; 7) Sleep-Disordered Breathing; and 8) Daytime Sleepiness. Caregivers are to answer based on the last week. If the last week was unusual for a specific reason, the caregiver should choose the most recent typical week. The answers to each question are provided by a choice of 3 markers: “Usually” if it occurs 5 or more times in a week; “Sometimes” if it occurs 2 to 4 times in a week; and “Rarely” if it occurs never or 1 time in a week. Some items should be reversed in scoring, so a higher score reflects more-disturbed sleep behavior. The caregiver is also asked to indicate for each item if the sleep item is a problem.

Study Code: GWND19002
EudraCT Number: 2019-001605-24
Clinical Protocol V2 18Dec19

9.2.12.3 36-Item Short Form

Caregivers' health-related QoL will be assessed using the SF-36 questionnaire. SF-36 measures 8 domains of health-related QoL within 8 scales: 1) limitations in physical activities because of health problems; 2) limitations in social activities because of physical or emotional problems; 3) limitations in usual role activities because of physical health problems; 4) bodily pain; 5) general mental health (psychological distress and well-being); 6) limitations in usual role activities because of emotional problems; 7) vitality (energy and fatigue); and 8) general health perceptions. The domains are used to calculate composite scores – physical health composite score (PCS) and mental health composite score (MCS). The scores for SF-36 are based on a 0-to-100 scale; 0 represents the lowest possible score, and 100 represents the highest possible score, with a higher score indicating a better health state.

9.2.12.4 Child Health Questionnaire Parent Form 50

The CHQ-PF50 is a generic QoL instrument designed and normed for children from 5 to 18 years of age. This instrument is a well-validated general QoL measure in pediatric populations with chronic illness. It measures the QoL of the child and the family by parent or child report. The caregiver will be asked to complete the questionnaire on behalf of the patient. The CHQ-PF50 covers multidimensional health concepts including Physical Functioning, Role/Social Limitations–Emotional/Behavioral, Role/Social Limitations–Physical, Behavior, Mental Health, Self-Esteem, General Health, Bodily Pain, Family Activities, Parent Impact–Time, Parent Impact–Emotional, and Family Cohesion. The CHQ-PF50 provides subscale scores as well as a Standardized Physical Summary (PhS) score and Standardized Psychosocial Summary (PsS) score. Scores are based on a 0-to-100 scale; a higher score indicates better QoL.

9.2.12.5 Hospital Services Use Questionnaire

This is a health utilization questionnaire designed to analyze the frequency of patient hospitalizations and hospital visits. Hospitalizations will also be recorded in the patient's CRF and through the serious adverse event (SAE) reporting process. The questionnaire will be completed via caregiver interview.

9.2.12.6 Caregiver Assessment of Rett Symptoms

Caregivers will be asked to rate, on a 0-to-10 numerical rating scale, the patient's condition and performance/severity of symptoms in terms of breathing, hand stereotypies, interactions, problem behaviors, constipation, seizures, and sleep. This assessment

Study Code: GWND19002

EudraCT Number: 2019-001605-24

Clinical Protocol V2 18Dec19

corresponds to the symptom diary completed weekly in the RCT but will be completed at trial visits only in the OLE.

9.2.12.7 Rett Syndrome Motor-Behavioral Assessment Scale

The MBA-9 scale is completed by the investigator and evaluates 9 RTT symptoms. MBA-9 was derived from the full MBA scale (37 RTT symptoms) by selecting the items that are deemed to be amenable to change and that reflect areas of meaningful clinical change. It includes 5 questions from the original Behavioral/Social Assessment, 1 question from the Orofacial/Respiratory Assessment, and 3 questions from the Motor Assessment/Physical Signs. The severity of the current symptoms are rated on a 5-point numerical scale: 0 = normal or never; 1 = mild or rare; 2 = moderate or occasional; 3 = marked or frequent; or 4 = very severe or constant. The total maximum score is 36, and higher total scores represent greater severity.⁶¹ The MBA-9 items address the core symptoms of RTT.

9.2.12.8 Clinical Global Impressions Questionnaire

The clinical global impressions (CGI) questionnaire was developed as a clinical trial measure to provide a brief, stand-alone assessment of the clinician's view of the patient's global functioning prior to and after initiating a study medication.⁵⁶

The CGI questionnaire is split into 2 scales: the CGI-S scale and the CGI-I scale. CGI-S is a 7-point scale that requires the clinician to rate the severity of the patient's illness at the time of assessment relative to the clinician's experience with patients who have the same diagnosis. Considering the total clinical experience, a patient will be assessed on the severity of illness at the time of rating. This is rated as follows: 1 = normal, not at all ill; 2 = borderline ill; 3 = mildly ill; 4 = moderately ill; 5 = markedly ill; 6 = severely ill; or 7 = extremely ill. The second scale, CGI-I, is a 7-point scale that requires the clinician to assess how much the patient's illness has improved or worsened relative to a baseline state at the beginning of the intervention (RCT Visit 2). This is rated as follows: 1 = very much improved; 2 = much improved; 3 = minimally improved; 4 = no change; 5 = minimally worse; 6 = much worse; or 7 = very much worse.

To ensure consistency, investigators will be instructed to complete the CGI referring to a predefined set of anchors developed specifically for the use of CGI in RTT.⁵⁹

The CGI-S and CGI-I assessments should be based on the entirety of the visit.

Study Code: GWND19002
EudraCT Number: 2019-001605-24
Clinical Protocol V2 18Dec19

9.2.12.9 Suicidality Assessment

The profound cognitive impairment of patients with RTT is such that the Children's Columbia-Suicide Severity Rating Scale is not considered appropriate in this trial. Instead, suicidality will be assessed by the investigator via a clinical interview with the caregiver.

9.2.13 Tanner Staging

The pubic hair growth and breast development of all adolescent patients (i.e., ≥ 7 years of age⁷¹ at the time of signing the ICF or earlier, if clinically indicated by the onset of menarche or other signs of precocious puberty) will be assessed using Tanner Staging.⁷² The assessment can either be performed by examination during the study visit or the appropriate Tanner Stage can be indicated by the caregiver, with reference to the chart provided.'

Once a patient reaches a score of V (i.e., 5) the assessment need not be performed again.

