Appendix 3.6 Tanner Staging

Tanner Staging⁷² is to be completed by all female adolescent patients (i.e. ≥ 7 years or 7 to less than 18 years of age⁷¹ at the time of signing the informed consent/assent form or earlier, if clinically indicated by onset of menarche or other signs of precocious puberty).

Female Development and Pubic Hair

Please check the box next to the most appropriate stage; in the event that qualifying characteristics are not within the same stage, defer to the lesser stage as the overall Tanner Score.

Tanner Stage 1 (Prepubertal, typically 10 years and younger)

- No glandular tissue; areola follows the skin contours of the chest.
- No pubic hair at all.

Tanner Stage 2 (10 to 11.5 years)

- Breast bud forms, with small area of surrounding glandular tissue; areola begins to widen.
- Small amount of long, downy hair with slight pigmentation on the labia majora.

Tanner Stage 3 (11.5 to 13 years)

- Breast begins to become more elevated and extends beyond the borders of the areola, which continues to widen but remains in contour with surrounding breast.
- Hair becomes more coarse and curly and begins to extend laterally.

Tanner Stage 4 (13 to 15 years)

- Increased breast size and elevation; areola and papilla form a secondary mound projecting from the contour of the surrounding breast.
- Adult-like hair quality, extending across pubis but sparing medial thighs.

Tanner Stage 5 (15+ years)

- Breast reaches final adult size; areola returns to contour of the surrounding breast, with a projecting central papilla.
- Hair extends to medial surface of the thighs.

Study Code: GWND19002
 EudraCT Number: 2019-001605-24
 Clinical Protocol V1 09Aug19

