6.2 Exclusion Criteria

If the RCT 'End of Treatment'/'End of Taper Period' visit assessments or Visit 1 reassessments (as applicable) raise any safety concerns, the investigator should consider whether it will be appropriate for the patient to continue to participate in the OLE trial or if the patient should be withdrawn. The patient may not enter the trial if ANY of the following apply:

- 6.2.1 Patient meets the withdrawal criteria (including clinically significant abnormal laboratory values) in the investigator's opinion (refer to [Section 10](#)).

Study Code: GWND19002
EudraCT Number: 2019-001605-24
Clinical Protocol V2 18Dec19

- 6.2.2 Patient met during the RCT the criteria for permanent IMP discontinuation (unless in case of an AE, if AE was not considered related with the IMP; patients that met ALT/AST elevations discontinuation criteria must be excluded).
- 6.2.3 Female patient is of childbearing potential, unless willing to ensure that they or their partner use a highly effective method of birth control (e.g., combined [estrogen and progestogen containing] hormonal contraception^a associated with inhibition of ovulation [oral, intravaginal or transdermal], progestogen-only hormonal contraception^a associated with inhibition of ovulation [oral, injectable or implantable^b] intrauterine devices/hormone-releasing systems^b, bilateral tubal occlusion^b, vasectomized partner^{b,c}, sexual abstinence^d during the trial and for 3 months after the last dose.
- 6.2.4 Patient has been previously enrolled and dosed in this trial.
- 6.2.5 Patient is unwilling to abstain from donation of blood during the trial.
- 6.2.6 Male participants who are fertile (i.e., after puberty unless permanently sterile by bilateral orchidectomy) and with a partner of childbearing potential unless agree to ensure that they use male contraception (e.g., condom) or remain sexually abstinent^d during the trial and for 3 months after the last dose.

^a The effect of GWP42003-P on oral contraceptives has not been investigated. GWP42003-P is not an inducer of CYP3A4 and therefore is not expected to alter the PK of hormonal contraceptives.

^b Contraception methods that are considered to have low user dependency

^c Provided that partner is the sole sexual partner of the trial patient of childbearing potential and that the vasectomized partner has received medical assessment of the surgical success.

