13.1 Sample Size, Power, and Significance Levels

There is no formal sample size calculation for this trial. All patients with RTT who completed the randomized, double-blind, placebo-controlled trial (GWND18064) who wish to take GWP42003-P and who meet eligibility criteria can be included in this trial.

Approximately 252 patients will be enrolled.

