9.3.5 Growth and Development

IGF-1 levels will be analyzed as part of the clinical laboratory testing. IGF-1 levels will be summarized on a continuous scale, including change from baseline.

Change from baseline (RCT and OLE baseline) to the end of treatment visit for IGF-1 levels will also be plotted against the Tanner Stages, weight, and height recorded at baseline.

The pubic hair growth (both sexes), genital (males only) and breast (females only) development of all adolescent patients (i.e., ≥ 7 years of age at the time of signing the informed consent form, or earlier if clinically indicated by onset of menarche or other signs of precocious puberty) will be assessed using Tanner Staging. The assessment can either be performed by examination during the study visit or the appropriate Tanner Stage can be indicated by the caregiver, with reference to the chart provided.

Patients will be examined at Visit 8, Visit 10 and Visit 14 (end of treatment). Once a patient

reaches a score of V (i.e., 5) the examination need not be performed again.

Tanner Stages will be summarized on a categorical scale by Visit. Shift table will be created to display shifts from baseline.

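### For boys, Protocol V2 Section 9.2.13 and SAP Section 9.3.5 name different Tanner components, and the SAP then pools the sexes

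*Protocol*

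**What the plan says.** Protocol V2 covers boys. Exclusion criterion 6.2.6 concerns "Male participants who are fertile (i.e., after puberty unless permanently sterile by bilateral orchidectomy", and the contraception section opens a matching requirement with "To be eligible for the trial, male participants who are fertile". SAP Section 3.3 describes the population as female or male.

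On puberty, V2 Section 9.2.13 says "The pubic hair growth and breast development of all adolescent patients" will be assessed by Tanner staging, either by examination or by the caregiver "with reference to the chart provided". It makes no distinction by sex. V2 does not reproduce the chart; its list of appendices contains only the schedule and the personnel details.

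SAP Section 9.3.5 gives the components as "The pubic hair growth (both sexes), genital (males only) and breast (females only) development of all adolescent patients". It plans a categorical summary of Tanner stage by visit, a shift table from baseline, and plots of change in IGF-1 against baseline Tanner stage. None of these is split by sex or by component.

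Tanner staging belongs to the growth and development item of the primary safety endpoint (V2 Sections 4.1.1 and 13.6.2; SAP Section 2.2.2).

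**The concern.** V2 brought in male-specific eligibility and contraception rules but left a Tanner procedure that fits girls. The two governing documents therefore ask for different measurements in the same patients. A site following the protocol would stage breast development in a boy, which says nothing about his puberty, and would not stage genital development. The analyst following the SAP would look for genital stage and have no use for the breast stage.

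The pooled outputs make this harder to see. A single Tanner stage for a boy and one for a girl would share the same rows although they rest on different components, or on a component that does not apply. Neither V2 nor the SAP says how component stages become the one stage that is tabulated and that ends further assessment at stage V.

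**Working it through.** **1. Which texts govern.** The SAP's Overview ties it to protocol version 2.0 of 18 December 2019 and to Annex 1 version 2. The annex adds Tanner staging at Visit 1 for late entrants but does not redefine its components. The comparison is therefore V2 Section 9.2.13 against SAP Section 9.3.5.

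**2. Components side by side.**

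| Component | V2 girls | SAP girls | V2 boys | SAP boys |
|---|---|---|---|---|
| Pubic hair | yes | yes | yes | yes |
| Breast | yes | yes | yes | no |
| Genital | no | no | no | yes |

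For girls the documents agree on all three rows. For boys they agree on one row (pubic hair) and disagree on two.

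**3. Is the difference acknowledged?** SAP Section 9.5 describes the early stop, the annex entrants and the added OLE baseline. It does not mention Tanner components.

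**4. Where it reaches the output.** Scheduled staging is at Visits 8, 10 and 14, plus Visit 1 for late entrants under the annex. The results feed the by-visit summary, the shift table and the IGF-1 plots, all pooled over sex.

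**5. Scale.** No stated figure depends on this point, so there is none to reproduce: "There is no formal sample size calculation for this trial", and the only number is an expectation, "Approximately 252 patients will be enrolled", with no split by sex. The protocol's disease section describes the syndrome as uncommon in males but gives no share. Taking the male share p as an assumption:

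- expected males = 252 × p
- chance of at least one male = 1 − (1 − p)^252

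| Assumed p | Expected males | Chance of at least one |
|---|---|---|
| 0.2% | 0.5 | 40% |
| 0.5% | 1.3 | 72% |
| 1% | 2.5 | 92% |
| 2% | 5.0 | 99% |
| 5% | 12.6 | about 100% |

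These are males of any age at full planned enrolment. Routine staging starts at age 7 and the trial was stopped early, so the number of boys staged would be smaller. The table shows scale only; the documents do not support any one row.

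**The case against.** The SAP says it also drew on sample data collection documents. Its sex-specific wording may simply reflect the eCRF or the chart in use, in which case genital stage was collected and only the protocol sentence is out of date. The early-assessment trigger is not limited to menarche: it also allows other signs of precocious puberty, which covers boys. The trial was stopped prematurely, so amending Section 9.2.13 may no longer change what is collected. All data are listed by patient, so a reader could look up any boy individually.

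Much of this stands. The documents show a mismatch of text, not a proven gap in data, and the trigger wording is not at fault. But possible agreement with an unseen eCRF does not reconcile the two visible documents, and a listing does not make a pooled table interpretable.

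A reader might also infer that boys would be held at stage 1 throughout. The only Tanner form in the documents, V1 Appendix 3.6, tells the rater, when components disagree, to "defer to the lesser stage as the overall Tanner Score"; a boy with pubic hair at stage 4 and breast at stage 1 would then score min(4, 1) = 1. The documents do not support this as a finding. That form is superseded, is addressed to female patients only, and its rule appears nowhere in V2 or the SAP. It shows only why a derivation rule should be written down.

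**Conclusion.** The point holds as a contradiction between current texts. For male patients, V2 Section 9.2.13 specifies breast stage and omits genital stage, SAP Section 9.3.5 specifies the reverse, and SAP Section 9.5 is silent on it. The SAP's pooled presentation leaves the difference invisible.

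The size is small. It concerns one part of one item in a multi-part endpoint that is purely descriptive, and an unknown number of boys that may be zero. Three further inferences should be resisted:

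- That boys' pubertal data will be wrong or absent, or that every boy is mis-staged. Pubic hair stage is specified for boys in both documents and is usable, assuming the eCRF holds it as its own item.
- That the SAP plans an analysis of male genital stage. It says the component is assessed, but its outputs are generic Tanner tables.
- That a particular number of boys will be visible in those tables. No count or share of males is given.

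The conclusion rests on the wording alone. The chart and eCRF could narrow it to a documentation error.

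**What to change.** - **Protocol, chart and eCRF.** Align Section 9.2.13, the chart and the eCRF with SAP Section 9.3.5: pubic hair and breast in females, pubic hair and genital stage in males.
- **SAP Section 9.3.5.** Present Tanner summaries and shifts by sex, state how the single stage is derived from its components, and do not use breast stages recorded in males.
- **SAP Section 9.5.** If genital stage was not collected, say so, and report pubic hair stage only for males.

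The cost is one protocol sentence, one chart, the matching eCRF items and a by-sex split of existing tables. If a protocol amendment is no longer practical because the trial has stopped, the SAP changes alone deal with the reporting.
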